12.4.2 Open-Label Extension Effectiveness Analyses

Actual and change from Baseline results collected in the OLE Phase will be tabulated with summary statistics for continuous outcomes and frequencies and percentages for categorical outcomes. No p-values will be reported for the OLE Phase. Results will be tabulated for the total group. Baseline will be the pre-double-blind-treatment Baseline (identical to that used for the double-blind analyses).

The following endpoints will be summarized for OLE:

- ESS-CHAD score as rated by caregivers/parents
- CaGI-S for EDS
- CGI-S for overall clinical status related to PWS
- Behavior as measured by the ABC-2
- Behavioral and cognitive rigidity as measured by MERS-PWS
- Psychomotor function as measured by the Cogstate Detection test
- Attention as measured by the Cogstate Identification test
- Working memory as measured by the Cogstate One Back test
- Measure of caregiver burden using ZBI-22
- Total score of the HQ-CT in conjunction with the FSZQ
- Cogstate Psychomotor/Attention Composite Score
- Cogstate Psychomotor/Attention/Working Memory Composite Score

The following endpoints will only be collected for the first year of the OLE study (i.e., at Visit 6 [Month 4], Visit 7 [Month 6], Visit 8 [Month 9] and Visit 9 [Month 12]):

- Behavior as measured by the ABC-2
- Behavioral and cognitive rigidity as measured by MERS-PWS
- Psychomotor function as measured by the Cogstate Detection test
- Attention as measured by the Cogstate Identification test
- Working memory as measured by the Cogstate One Back test
- Measure of caregiver burden using ZBI-22
- Total score of the HQ-CT in conjunction with the FSZQ
- Cogstate Psychomotor/Attention Composite Score
- Cogstate Psychomotor/Attention/Working Memory Composite Score

The following endpoints will be collected until the end of the study:

- ESS-CHAD score as rated by caregivers/parents
- CaGI-S for EDS
- CGI-S for overall clinical status related to PWS

In addition, the same categorical summaries provided for the Double-Blind Treatment Phase will be provided for:

- ESS-CHAD score as rated by caregivers/parents
- CaGI-S for EDS
- CGI-S for overall clinical status related to PWS

12.5 PK Analyses

Plasma concentration-time data of pitolisant and BP1.3484 will be summarized using descriptive statistics by age group (6 to <12 years; 12 to <18 years, ≥18 years), treatment group, and scheduled sampling interval. The following summary statistics will be included for plasma concentration-time data: mean, SD, coefficient of variation (CV%), geometric mean, geometric SD, median, minimum, and maximum.

Plasma concentration-time profiles of pitolisant and BP1.3484 will be plotted on semi-log and linear scales for each individual patient as spaghetti plots by age group (6 to <12 years; 12 to <18 years, ≥18 years) and treatment group using actual collection times. For ease of presentation, mean plasma concentration-time data of pitolisant and BP1.3484 will be plotted separately by midpoint (on hour scale) for the planned interval on both linear and semi-logarithmic scales. Plasma PK concentrations of pitolisant and BP1.3484 for each individual will be reported to the precision of the raw data in listing presentations. In addition, concentration-time profiles for each analyte will be plotted by patient.

Values reported as below the lower limit of quantification (LLOQ) or below the limit of quantification (BLQ) i.e., reported as <LLOQ (BLQ) will be imputed to be 0.

If data allow, the following steady-state PK parameters will be calculated for each analyte as listed in Table 12.

Table 12: PK Parameters

Parameter	Description	PK Analysis Notes	Analyte	SAS Programming Notes
C _{max}	Maximum plasma concentration. Observed peak analyte concentration obtained directly from the experimental data without interpolation, expressed in concentration units.		Pitolisant and BP1.3484	Cmax from WinNonLin software (WNL) version 8.1.1 or later.
T _{max}	Time to reach C _{max} in plasma. The time to reach maximum concentration is obtained directly from the experimental data without interpolation and expressed in time units.		Pitolisant and BP1.3484	Tmax from WNL
AUC _(0-T)	Area under the concentration-time curve from time 0 (dosing) to the time of the last quantifiable concentration observed, without interpolation or extrapolation, using trapezoidal summation. AUC _(0-T) is expressed in concentration*time units.	Calculated by the linear up/log down method in WNL	Pitolisant and BP1.3484	AUClast from WNL
AUC _(tau)	Area under the {plasma / serum} concentration-time curve over the sampling interval (time 0 to XXhr) using trapezoidal summation. The actual duration of tau is used to capture this parameter. To capture AUC _{tau} , the actual time deviation should be <10%.	Calculated by the linear up/log down method in WNL	Pitolisant and BP1.3484	AUC from WNL summary file at corresponding midpoint XX Flag to List only if: Percent difference in planned and actual sampling at tau ≥10%
C _{max} /D	Dose normalized maximum plasma concentration.		Pitolisant	Cmax / dose

Parameter	Description	PK Analysis Notes	Analyte	SAS Programming Notes
AUC _(0-T) /D	Dose normalized area under the concentration-time curve from time 0 (dosing) to the time of the last quantifiable concentration observed.	Calculated by the linear up/log down method in WNL	Pitolisant	AUClast / dose
C _{trough}	Observed plasma concentration immediately prior to dose.		Pitolisant and BP1.3484	Predose concentration (Day 22, 50, 77)

PK parameters will be summarized overall and by treatment group and age. The following summary statistics will be included for plasma concentration-time data: mean, SD, CV%, geometric mean, geometric SD, median, minimum, and maximum. Only the median, minimum, and maximum will be calculated for t_{max}.

The plasma concentration-time data from this study may be combined with data from previous studies that utilized the same bioanalytical method, and population PK analyses may be conducted as post hoc analysis; results will be provided in a separate report.

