- ^u Patients will be instructed to take study drug once daily in the morning upon wakening; exception is on the morning of Visit 4, when study drug administration will be at the study site, with the timing of administration based on the PK sampling schedule. Patients will be instructed to record in the study drug dosing section of the study diary (with the

assistance of their caregiver if needed) the number of tablets administered from each bottle daily (Appendix B); the time of study drug dosing will be recorded on the day before Study Visit 4.

- ^v Blood sample collection for PK analyses at Visit 3 and Visit 5 may be at any time after the morning dose of study drug and samples may be collected at the same time as the clinical laboratory sample (including the fasting ghrelin sample at Visit 5). Time of last dose of study drug and time of blood sample collection for PK analyses must be recorded.
- w Patients and/or their caregiver will be instructed to record in the study drug dosing section of the study diary the time of day that they take study drug on the day before Visit 4. On the day of Visit 4, **patients will not take their daily dose of study drug before arriving at the study site.** Study drug administration will be at the study site and timing will be based on the PK sampling schedule. At the study site, a blood sample for PK analyses will be collected before administration of the daily dose of study drug. The time of study drug administration will be recorded. Blood sample collection for PK analyses will be at the following times after study drug administration: between 45 and 75 minutes after dosing, between 1.5 and 2.5 hours after dosing, between 3.0 and 4.0 hours after dosing, and between 5.0 and 6.0 hours after dosing. The time of each blood sample collection for PK analyses is to be recorded. The total volume of blood collected is not to exceed the maximal allowable of 3.0 mL/kg per day (Appendix A and Table 10).
- ^x To familiarize patients with the Cogstate Computerized Cognitive Test Battery, the tests are to be administered twice during Screening with a break of at least 15 minutes between battery administrations.

Assessments associated with on-site study visits during the Double-Blind Treatment Phase may be completed remotely under the oversight of the Investigator, as detailed in Section 6.6.

SCHEDULE OF ASSESSMENTS OPEN-LABEL EXTENSION PHASE

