7.3.2.1. Visit 3 (Day 22 \pm 3 Days)

The patient (with the assistance of their caregiver if necessary) should record in the study diary the time of study drug dosing on the morning of Visit 3. The following evaluations will be performed at Visit 3:

- Urine pregnancy test (FCBP only)
- Abbreviated physical examination
- Body weight
- Vital signs
- 12-lead ECG (in triplicate)
- C-SSRS (Appendix M)
- ADAMS
- Clinical laboratory tests (serum chemistry, hematology, urinalysis)
- Blood sample collection for PK analyses (sample may be collected at the same time as clinical laboratory tests; time of last dose of study drug and time of blood sample collection to be recorded) (Section 6.4).
- Review of AEs
- Review of concomitant medications
- ESS-CHAD (parent/caregiver version)
- CaGI-S (for EDS)
- CGI-S (for overall clinical status related to PWS)
- ABC-C
- MERS-R-PWS
- ZBI-22
- HQ-CT
- FSZQ
- Review study drug compliance/accountability (Section 5.5 and Section 5.6)

Patients will be dispensed study drug at this visit.

7.3.2.2. Telephone Calls; TC 3, TC 4, and TC 5 (Days 29, 36, and 57 [±3 Days])

Patients and/or their caregivers will be contacted by the study site by telephone on Days 29, 36, and 57 (±3 days; TCs 3, 4, and 5, respectively) to assess for AEs and use of concomitant

medications, complete the C-SSRS, ADAMS, and confirm compliance with administration of study drug.

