Visit 5 (Day 77 ± 3 days) is the EOT visit in the Double-Blind Treatment Phase of the study. A fasting blood sample for ghrelin testing will be collected at this visit; therefore, the patient should fast on the night before Visit 5. The patient (with the assistance of their caregiver if necessary) should record in the study diary the time of study drug dosing on the morning of Day 77, Visit 5. The following evaluations will be performed at Visit 5:

- Urine pregnancy test (FCBP only)
- Urine drug screen
- Full physical examination
- Body weight and height
- Vital signs
- 12-lead ECG (in triplicate)
- C-SSRS (Appendix M)
- ADAMS
- Clinical laboratory tests (serum chemistry, hematology, urinalysis); may be collected with the fasting serum ghrelin measurement and the PK blood sample collection
- Serum ghrelin measurement (fasting)
- Blood sample collection for PK analyses (sample may be collected at the same time as clinical laboratory tests and fasting serum ghrelin measurement; time of last dose of study drug and time of blood sample collection for PK is to be recorded)
- Review of AEs

- Review of concomitant medications
- ESS-CHAD (parent/caregiver version)
- CaGI-S (for EDS)
- CGI-S (for overall clinical status related to PWS)
- ABC-C
- MERS-R-PWS
- Cogstate Detection Test
- Cogstate Identification Test
- Cogstate One Back Test
- ZBI-22
- HO-CT
- FSZQ
- Review study drug compliance/accountability (Section 5.5 and Section 5.6)

Patients will be given the opportunity to participate in the OLE Phase at this visit. Eligible patients who enter the optional OLE Phase will be dispensed open-label pitolisant (Section 5.2.2); eligibility criteria must be confirmed before patients receive open-label pitolisant. Patients will be instructed to begin taking open-label pitolisant on the following day in the morning upon wakening (Day 78 ± 3 days).

Patients who do not enter the OLE Phase will be receive Safety Follow-up TCs from the study site 15 days (\pm 3 days) and 30 days (\pm 3 days) after last dose of blinded treatment, as outlined in Section 7.5.

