D11	Visit 3	Visit 3 (Day 22)	22	2	35
Double- Blind	Visit 4	Visit 4 (Day 50)	50	36	63

Abbreviations: ABC-2 = Aberrant Behavior Checklist, Second Edition; ADAMS = Anxiety, Depression, and Mood Scale; C-SSRS = Columbia-Suicide Severity Rating Scale; CAGI-S = Caregiver Global Impression of Severity; CGI-S = Clinical Global Impression of Severity; ECG = electrocardiogram; ESS-CHAD = Epworth Sleepiness Scale for Children and Adolescents; FSZQ = Food Safe Zone Questionnaire; HQ-CT = Hyperphagia Questionnaire for Clinical Trials; MERS-PWS = Montefiore-Einstein Rigidity Scale – Prader-Willi Syndrome; PWS = Prader-Willi Syndrome; ZBI-22 = 22-item Zarit Burden Interview.

Note: For MSLT, C-SSRS and ADAMS no analysis window will be applied; data will be reported using the nominal visit.

Table 6: PK Draw Timing

Visit	Target Day		
Visit 3	Day 22	Any time after the morning dose of the study drug	
Visit 4	Day 50	 Pre-dose Between 45 and 75 minutes after dosing, Between 1.5 and 2.5 hours after dosing, Between 3.0 and 4.0 hours after dosing, Between 5.0 and 6.0 hours after dosing 	
Visit 5	77	Any time after the morning dose of the study drug	

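### SAP Table 12 takes Ctrough from predose samples on Days 22, 50 and 77, but only the Visit 4 (Day 50) profile has a scheduled predose sample

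*SAP*

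**What the plan says.** SAP Section 12.5, Table 12, defines Ctrough as "Observed plasma concentration immediately prior to dose" for both pitolisant and BP1.3484. Its programming note gives the source as "Predose concentration (Day 22, 50, 77". The parameters in Table 12 are to be calculated where the data permit, and are summarised overall, by treatment group and by age.

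SAP Section 9.2.1, Table 6, gives the draw time for Visit 3 and for Visit 5 as "Any time after the morning dose of the study drug". It lists a predose draw only for Visit 4. The protocol's Schedule of Assessments for the Double-Blind Treatment Phase agrees in footnote v: "Blood sample collection for PK analyses at Visit 3 and Visit 5 may be at any time after the morning dose of study drug". SAP Appendix 7, footnote v, repeats this.

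The dosing instructions match that timing. Protocol Section 7.3.2.1 asks for a diary record of "the time of study drug dosing on the morning of Visit 3", and Section 7.3.2.4 asks for "the time of study drug dosing on the morning of Day 77, Visit 5". Schedule footnote u tells patients to dose on waking, and adds: "exception is on the morning of Visit 4, when study drug administration will be at the study site". At Visit 4, a sample is taken before the on-site dose and four more are taken after it (footnote w and Section 7.3.2.3).

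**The concern.** The definition in Table 12 and its list of days cannot both be met from the planned samples. The table is the instruction from which the parameter will be programmed, and the SAP has no rule that keeps the Visit 3 and Visit 5 samples out of Ctrough. A programmer who selects records by study day would place post-dose values under that label on two of the three days. Draw time after the dose is open at those visits, so the excess over a true trough would vary between patients and would also widen the spread of the summary. A programmer who applies the definition instead would return empty cells on those days. Two competent people could therefore produce different tables from the same text.

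**Working it through.** **Step 1. Number of PK samples per visit.** Protocol Section 6.4 sets 4.0 mL per PK sample, and Table 10 gives PK volumes of 4, 20 and 4 mL at Visits 3, 4 and 5. Samples = volume / 4.0 mL:

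- Visit 3: 4 / 4.0 = 1
- Visit 4: 20 / 4.0 = 5, which matches the five samples stated under Table 10
- Visit 5: 4 / 4.0 = 1

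The blood budget leaves no room for a second, predose draw at Visit 3 or Visit 5.

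**Step 2. Class each scheduled sample by timing** (SAP Table 6; schedule footnotes v and w).

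| Visit (day) | Scheduled samples | Predose | Post-dose | Listed for Ctrough in Table 12 |
|---|---|---|---|---|
| 3 (22) | 1 | 0 | 1 | yes |
| 4 (50) | 5 | 1 | 4 | yes |
| 5 (77) | 1 | 0 | 1 | yes |
| Total | 7 | 1 | 6 | |

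Only 1 of the 3 listed days has a scheduled sample that meets the definition.

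**Step 3. Illustrative size if a post-dose sample were used.** The documents give no half-life or absorption rate for pitolisant, so these are assumptions: one compartment at steady state, dosing every 24 h, absorption rate ka = 1/h, half-life 8 to 20 h (k = ln 2 / half-life), and a sample 1 to 3.5 h after dosing. The ratio to trough is

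R(t) = [e^(−kt)/(1 − e^(−24k)) − e^(−ka·t)/(1 − e^(−24ka))] / [1/(1 − e^(−24k)) − 1/(1 − e^(−24ka))]

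- Half-life 8 h: the denominator is 1.1429 − 1.0000 = 0.1429.
  - R(1) = (1.0480 − 0.3679)/0.1429 = 4.8
  - R(2.5) = (0.9203 − 0.0821)/0.1429 = 5.9, which is the peak
  - R(3.5) = (0.8439 − 0.0302)/0.1429 = 5.7
- Half-life 20 h: the denominator is 1.7708 − 1.0000 = 0.7708.
  - R(1) = (1.7105 − 0.3679)/0.7708 = 1.7
  - R(3.5) = (1.5685 − 0.0302)/0.7708 = 2.0, essentially the peak

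The range over 1 to 3.5 h is therefore about 1.7 to 5.9.

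**Step 4. Sensitivity.** With ka between 0.5 and 2/h, the same interval gives about 1.4 to 6.7. With ka = 1/h, a sample at 15 minutes gives 1.3 to 2.4, one at 8 h gives 1.7 to 4.0, and one at 10 h gives 1.6 to 3.4. The factor depends heavily on sampling time. The model describes an absorbed parent drug and says nothing quantitative about BP1.3484.

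**The case against.** The best defence is that Table 12 does not tell anyone to use a post-dose value. Both its definition and its note require a predose concentration, and Section 12.5 makes the calculation conditional on the data. Dose and sample times must be recorded, so a post-dose sample can be recognised. On that reading Days 22 and 77 are simply empty. This stands to the extent that mislabelling is possible but not certain. It does not rescue the cell, which would then list two days for which nothing is scheduled.

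A second point also stands. Protocol Section 6.6.1.2 and Table 13 allow a Visit 4 profile that was not collected to be taken at the next on-site visit, at an unscheduled visit or at Visit 5. Some patients could therefore have a genuine predose sample near Day 77, and a rule limited to Day 50 would discard it. Such a sample is not guaranteed to be predose either, because Section 7.3.2.4 has patients record a dose taken on the morning of Visit 5. The recorded times have to decide.

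A reader might infer that the trial will report false troughs and so misjudge steady state or accumulation across Days 22, 50 and 77. The documents do not support that. Neither plans an accumulation ratio, a test of steady state or a comparison of Ctrough between visits. The listed PK endpoints (Protocol Section 3.2.2; SAP Table 3) are Cmax, AUClast and tmax. The exposure-response plots in SAP Section 12.4.1.6.6 use concentration over time, not Ctrough.

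Part of the remedy is also in place. SAP Table 6 already labels these draws as post-dose, and Section 12.5 plots individual profiles by actual collection time.

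**Conclusion.** The inconsistency is real and rests on the documents alone: as written, the Ctrough source is wrong for two of its three days. The consequence is either post-dose concentrations in the Ctrough summaries or empty summaries on those days, and the SAP does not settle which. The illustrative 1.7- to 5.9-fold excess depends on the assumed kinetics and on sampling 1 to 3.5 h after the dose, a time that the protocol leaves open. It shows that the error would not be trivial if it occurred, and should not be read as an estimate for this trial. The effect is confined to a supportive, descriptive parameter. No efficacy conclusion and no listed PK endpoint is affected.

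**What to change.** Replace the Ctrough programming note in SAP Table 12 with: predose sample of the Visit 4 PK profile, whenever collected (including if moved to an unscheduled visit or Visit 5), confirmed predose from the recorded dose and sample times.

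Add one sentence to Section 12.5: the single Visit 3 and Visit 5 samples are reported as post-dose concentrations by actual time since last dose, and are excluded from Ctrough.

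The cost is one table cell and one sentence. The protocol already requires the dose and sample times to be recorded, so no new data, procedure or dosing change is needed. No information is lost, because the Visit 3 and Visit 5 values are still reported and a relocated predose sample is kept.

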12.6 Safety Analyses

All safety analyses will be completed for the Double-Blind safety and Open-Label safety populations. All safety data will be listed and summarized. No formal statistics will be performed for the safety analysis.

For the Double-Blind Treatment Phase, summaries will be presented by treatment arms and active arms pooled; for the OLE Phase, results will be tabulated for the overall group.

12.6.1 Adverse Events

An AE is defined as any untoward medical occurrence associated with the use of a drug in humans, whether or not considered drug related.

A TEAE is defined as any event not present before exposure to study drug or any event already present that worsens in intensity or frequency after exposure and up to 30 days after the last dose of study drug. For the OLE Phase, any AE starting on or after the first dose of OLE treatment will be considered treatment emergent.

A serious AE (SAE) is defined as any AE that results in any of the following outcomes: death, is life-threatening, results in inpatient hospitalization or prolongation of existing hospitalization, results in a persistent or significant incapacity or substantial disruption of the ability to conduct normal activities of daily living, or is a congenital anomaly/birth defect. Important medical events that may not result in death, be life-threatening, or require hospitalization may be considered SAEs when, based upon appropriate medical judgment, they may jeopardize the patient and may require medical or surgical intervention to prevent one of the outcomes listed in this definition.

The AE's relationship to study treatment will be evaluated by the investigator. The following relationships will be collected in eCRF: definitely related, probably related, possibly related,

unlikely related, or not related. The AEs that are evaluated as definitely, probably, or possibly related (or with missing relationship) will be considered treatment-related AEs for summary purposes.

The severity of AEs will be classified by the investigator as mild, moderate, or severe. If the severity is missing, the AE will be assumed to be severe.

An overall AE summary will be generated presenting the frequency and percentage of patients and the number of AEs for the following categories. This overall summary will also be provided for each age groups (6 to <12 years; 12 to <18 years and 18 years or older) for the Double-Blind Treatment Phase. The same summary may be repeated for the OLE Phase.

- Any TEAE
- Any treatment-related TEAE
- Any severe TEAE
- Any treatment-related severe TEAE
- Any serious TEAE
- Any treatment-related serious TEAE
- Any TEAE leading to study discontinuation
- Any TEAE leading to discontinuation of investigational product (IP)
- Any TEAE leading to discontinuation of IP and leading to study discontinuation
- Any TEAE leading to interruption of IP
- Any TEAE leading to death

All AEs will be coded using MedDRA; the version used will be included in the tables and listings footnotes. The TEAEs will also be summarized by system organ class (SOC), preferred term (PT), and (where applicable) by severity.

The TEAE summary tables will be sorted by SOC and PT. SOCs will be displayed in descending order of overall frequency and then alphabetically. PTs will be displayed in descending order of overall frequency and then alphabetically within SOC. A patient with 2 or more events within the same SOC or PT will be counted only once in that level using the most severe incident or most related incident. Percentages will be based on the number of patients in the safety population.

The following summaries by SOC and PT will be provided:

- TEAE
- Treatment-related TEAE
- TEAE by maximum severity
- Serious TEAE
- Treatment-related serious TEAE
- TEAE leading to discontinuation of IP

- TEAE leading to interruption of IP
- TEAE leading to death

In addition, all AEs and all SAEs (regardless of treatment-emergent status) will be tabulated by SOC and PT.

Finally, the following summaries by SOC and PT will be provided for each age groups (6 to <12 years; 12 to <18 years and 18 years or older) for the Double-Blind Treatment Phase. The same summaries by age groups may be repeated for the OLE Phase.

- TEAE
- Treatment-related TEAE
- TEAE by maximum severity

All AEs will be presented in a data listing. Separate data listings will be generated for treatment related AEs, SAEs, AEs leading to death and AEs leading to study discontinuation.

For patients who opt to continue in the OLE Phase of the study, only AEs starting strictly before the first dose in the OLE Phase will be summarized for the Double-Blind Treatment Phase, and any AEs that started on or after the first dose of treatment in the OLE Phase and up to 30 days after the last dose of treatment in the Double-Blind Treatment Phase will be included in a separate listing (for the OLE Phase reporting); these AEs will be included in the OLE Phase summaries. A listing of all the AEs that were ongoing (i.e. that are ongoing or have a stop date after the first dose of treatment in the OLE Phase) at the end of the Double-Blind Treatment Phase will be included in the OLE Phase reporting to capture additional information for those AEs (such as end date and potential treatments) and patients will not necessarily be on the same treatment as what they were randomized to in the Double-Blind Treatment Phase.

For the OLE Phase, the same data summaries and listings will be produced. The data will be tabulated for overall and by period

. Calculations for AE start and stop dates are detailed in Appendix 5.

